# Emergency Medicine Prospective Protocol

**Study Phase:** Study Text Messages (During Months 1-12)

**Study Group:** All participants

**Setting:** Remote (text messages via caregiver's mobile device)

**Timing:** Study procedures will occur each month

## Study text messages:

No matter which group caregivers are randomly assigned to, all study subjects will receive monthly text messages from our team while they are taking part in the study (12 months).

- Group 1 (control): They will get about 3-4 text messages each month. Messages will include:
  - Reminders for upcoming follow-up visits
  - Feedback related to the photos they send us of their child riding in their car
  - General study info
- Group 2 (TCBD intervention): They will get about 5-6 custom text messages. Messages will include:
  - Reminders for upcoming follow-up visits
  - Feedback related to the photos they send us of their child riding in their car
  - Tailored text messages --Custom tips and info based on their answers to study surveys
- **\*\*See section 9 of IRB app, "supporting documents" for a document called, "TCBD library and error messages" and refer to the sheet labeled, "general message library.** This document provides a library of custom tips/general supportive and informational text messages that the TCBD intervention group may receive over the course of the study (12 months). Participants will receive these text messages as applicable based on their answers within the surveys, based on the time of year as well as priority of message content.

**Study Phase:** Follow-ups --Month 6 and Month 12

**Study Group:** All participants

**Setting:** In-person or remote (via photo submission/video chat, phone)

**Timing:** Within 1 month

## 6- and 12-month follow-up visits:

- All subjects will be asked to complete a 6- and 12-month (follow-up) visit.
- The follow-up visits include:
  - Taking an online follow-up survey (about 20-25 minutes) --the 6 month follow-up survey will also include a health literacy assessment called the Newest Vital Sign. These questions will not be asked during the 12 month survey.
  - Completing an in-person Tiny Cargo check-in (about 10 minutes)
  - At the 6 month follow-up ONLY: Receiving a study handout on the car seat recommendations for children as put out by the National Highway Traffic Safety Administration (NHTSA) --**see section 9 of IRB app for a copy of the handout called, "NHTSA child passenger safety overview"**
- Survey: The follow-up survey can be done in person on an iPad, on the study participant's own device, or over the phone with a study team member. A team member will send them a link to take the survey so that they can do it before the visit. The follow-up survey will have questions that are like those asked on the baseline survey.
- Tiny Cargo Check-in: During the check-in, a study team member will look to see how their child usually rides while in their car. Every effort will be made to meet with the study participant and their child in person for the 6- and 12-month follow-up visit. This meeting can take place at Lurie Children's or at another location that is closer to them. If they are unable to meet with us in

# Emergency Medicine Prospective Protocol

person (e.g., they move out of state), they may also send us photos of their child as they usually ride in their car via text message or via a video chat (e.g., Facetime or google hangout).

- **\*\*See section 9 of IRB app, "supporting documents" for a document called, "TCBD text library and error messages" and refer to the sheet labeled, "Response to errors."** This document provides scripted responses that the RA will use when major misuse and/or errors are visible during the Tiny Cargo check-ins. The TCBD intervention messages are referred to as "Scripted MI response" while the control group's responses are referred to as "scripted control response."
- After the 6-month follow-up assessment, caregivers in the intervention group only who continue suboptimal CRS use will be re-randomized to receive either the basic or enhanced intervention.
- The enhanced TCBD intervention group will include one additional motivational interviewing (MI) session by phone in Month 7/8 and one to two additional tailored text messages in Months 7-12 (total of 7 tailored tips during these months compared to 4 tailored tips for those in the basic TCBD). The extra text messages will be sent to those in the enhanced TCBD group until size-appropriate restraint use is observed. Caregivers receiving enhanced TCBD will be encouraged to obtain a free seat check with a certified child passenger safety technician (CPST) in the community.
- The basic TCBD intervention group will continue on in study without any changes.

**Study Phase:** Phone Counseling Session --Month 7/8

**Study Group:** Enhanced TCBD Intervention Group

**Setting:** In-person or remote

**Timing:** Within 1 month

Phone counseling session (enhanced TCBD intervention):

After the study subject completes their 6-month follow-up visit, the study team will determine if the child is using the recommended child restraint system (car seat or booster seat) for their age and size. The intervention group subjects whose children are NOT using the recommended restraint will be randomly assigned (like flipping a coin) to one of two groups. They cannot pick the group they will be in.

The groups are:

- Group 2 (basic TCBD): They will keep taking part in the study with the basic intervention and nothing will change.
- Group 3 (enhanced TCBD): They will keep taking part in the intervention arm of the study but will be asked to talk with a Car Seat Coach (i.e., a behavioral research assistant trained for the study) by phone for about 20 minutes. The phone call will cover some of the challenges and successes they are having with traveling safely with their child. They will also get 1 or 2 additional study text messages each month. These extra text messages will include:
  - Feedback related to the photos they send us of their child riding in their car
  - Feedback related to survey answers

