## ***3.2 Allocation to Interventional Group***

After completing the baseline survey, all caregivers will be randomized into one of two groups: 1) TCBD intervention group, or 2) control group. Computerized, block randomization (block sizes from four to eight) will be applied to assign eligible caregivers to the TCBD intervention or control group in a 3:1 ratio. Blocks will be stratified by age groups related to child passenger safety recommendations (<2 years – rear-facing CRS, 2-4 years – forward-facing CRS, 5-10 years – booster seat) and the child passenger safety behavior that led to eligibility for study (not using the recommended restraint currently or planning a premature transition in the coming 6 months).

After the 6-month follow-up assessment, caregivers in the intervention group only who continue suboptimal CRS use will be re-randomized by computer in a 1:1 ratio to receive either the basic or enhanced intervention. The enhanced TCBD will include one additional motivational interviewing (MI) session by phone in Month 7/8 and one to two additional tailored text messages in Months 7-12 (total of 7 tailored tips during these months compared to 4 tailored tips for those in the basic TCBD). The extra text messages will be sent to those in the enhanced TCBD group until size-appropriate restraint use is observed. Caregivers receiving enhanced TCBD will be encouraged to obtain a free seat check with a certified child passenger safety technician (CPST) in the community. The primary outcomes (size-appropriate CRS use and CPaSS) will be assessed in-person at Months 6 and 12. The secondary outcome, the CPaSS trajectory, is a measure of correct and consistent restraint use in response to the intervention and will be assessed by scoring photographs submitted by caregivers (Months 1-5; 7-11).

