## 6 Statistical Plan

### 6.1 Sample Size and Power Determination

Briefly, our calculations are based on two-sample comparisons between groups (e.g., control and TCBD) using results from our pilot study that assessed percent size-appropriate child passenger safety behaviors at 6-month follow-up (referred to as the “response rate” below). For analyses involving multiple time points, these calculations represent a conservative lower bound on the power that would only be achieved if the effective sample equals 1 observation per person (i.e. perfect within-individual correlation). For the calculations below we assume: a) 17% response rate among controls; b) 25% response rate among TCBD caregivers at 6 Month (with 75% of TCBD caregivers re-randomized); and c) only 80% of the target sample (n=204 controls and n=516 TCBD in the initial dichotomy) will be available for analysis at follow-up. Components (a) and (b) are based on pilot data where the control group received generic educational materials and outcomes were assessed at 6-months. Component (c) is a conservative correction for attrition. For Aim 2, we estimated power while accounting for uncertainty in the group sizes by simulating response and re-randomization patterns according to the above probabilities and testing for significant between-group differences; this process was repeated 10,000 times and the power was estimated as the percent of replications in which a between-group difference was identified. Binary Outcome: For the binary response case, if the observed response rate is at least 29.4% among those receiving enhanced TCBD, it can be reliably (>80% power) distinguished from a control response rate of 17%. Analogously, a response rate of at least 27.6% among basic intervention would be reliably (>80% power) distinguished from control. Converted to Cohen's  $h$ , both differences reflect small-to-medium effect sizes ( $h = 0.30$  and  $h = 0.26$ , respectively). Numeric Outcome (CPaSS): If the standardized mean difference (i.e. Cohen's  $D$ ) is  $>0.25$  (a small-to-medium effect size), we can reliably distinguish between control and basic TCBD conditions. Similarly, if  $D \geq 0.28$ , a small-to-medium effect size, we will have sufficient power (80%) to distinguish the control and enhanced TCBD conditions. Aim 2: Monte Carlo studies of linear latent trajectory models indicate that a medium level of heterogeneity among the slopes and/or intercepts of the trajectories can be reliably recovered (power  $> 80\%$ ) with a total sample size of  $n=200$ , with power exceeding 95% when the level of heterogeneity is high; given that our sample size soundly exceeds 200, we expect sufficient ability to determine the underlying characteristic trajectory types. Nevertheless, we further justify our sample size with a brief simulation study. Assuming a final sample size of 720, conservatively assuming individuals are only measured at an average of 25% of the 12 monthly assessments, we simulate data from a population with four equally likely trajectory types: consistently low, consistently high, linearly decreasing, and starting high then dropping off. Because we have no basis for estimating variability in the score, we assumed mean/variance equivalence, consistent with the Poisson distribution. Due to the time required to fit such models, we only completed 200 simulation replications, where we were able to correctly conclude (based on BIC) that there were four

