## 6.2 Statistical Methods

All subjects, once randomized, will be included in an intention-to-treat analysis and outcomes will be collected even if the caregiver does not engage in the randomly assigned intervention. We will evaluate randomization by testing for covariate (e.g. demographic characteristics) balance between initial treatment groups, and between the re-randomized treatment groups created after the 6-month follow-up. If significant differences are observed, we will adjust for these variables or conduct stratified analyses. All statistical hypothesis tests and power calculations will use a two-sided = 0.05.

**Aim 1:** To test the efficacy of the TCBD intervention compared to usual care for improving primary outcomes [i.e., size-appropriate restraint (dichotomous) and CPaSS (numeric)] at 12 months. We hypothesize greater proportions of children will be using a size-appropriate restraint and higher CPaSS among caregivers in the intervention groups (basic and enhanced) compared with the control group (usual care) at the 12-month assessment. **Statistical Analysis:** Our primary analytic tool for estimating treatment effects will be generalized linear models (GLMs), and for analyses involving joint analysis of multiple follow-up data points, we will use generalized linear mixed models (GLMMs), which allows direct modeling of the correlations between data points (e.g. repeated measurements on individuals), and the inclusion of individuals with incomplete data (e.g. missing time points). The GLM(M) framework also allows simple controlling for confounders (if necessary) through their inclusion in the model as covariates. For the analysis of binary outcomes, we will use logistic GLM(M)s and for numeric outcomes (CPaSS-D) we will initially specify linear (Gaussian) GLM(M)s; this choice will be scrutinized by analyzing model diagnostics. The primary inferential target will be the coefficient for the treatment group indicator, making this effectively equivalent to ANCOVA. Adjustment for the baseline measurement is important for guarding

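### The plan has no rule for TCBD caregivers who miss Month 6 and return at Month 12, so the enhanced group holds only Month-6 attenders while control does not

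*Combined protocol and SAP*

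**What the plan says.** Under the Month 7/8 phone session in section 3, the order is fixed: "After the study subject completes their 6-month follow-up visit, the study team will determine if the child is using the recommended child restraint system". Section 3.2 adds that "caregivers in the intervention group only who continue suboptimal CRS use will be re-randomized by computer in a 1:1 ratio". Control caregivers pass through no such step. Sections 3.1 and 5.1.1 describe the first randomisation as being to basic TCBD or control.

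The Aim 1 hypothesis in 6.2 concerns the basic and enhanced groups, each set against control at Month 12, and 6.1 gives separate power for enhanced v control and basic v control. Section 6.1 assumes "25% response rate among TCBD caregivers at 6 Month (with 75% of TCBD caregivers re-randomized", so responders and re-randomised caregivers together make up the whole TCBD arm. It also assumes that "only 80% of the target sample (n=204 controls and n=516 TCBD in the initial dichotomy) will be available for analysis at follow-up", without saying which follow-up is meant.

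Section 6.2 promises intention-to-treat, and 8.2 says multiple imputation may be used. Neither places a caregiver without a Month-6 result in a second-stage group.

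**The concern.** A caregiver with no Month-6 assessment is neither a responder nor a candidate for re-randomisation, and so can never be in the enhanced group. A control caregiver who misses Month 6 and returns at Month 12 is analysed as control all the same. Attendance at Month 6 thus becomes a condition of membership in one group and not in the other, and missing a visit may well be related to restraint use.

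The same caregivers stay in basic TCBD by default, or could be set aside, because the plan does not say. Either choice changes the make-up of the basic group in a comparison named in the primary hypothesis, and the choice could be made after the data are seen. The power section has no category for these caregivers, so its enhanced sample depends on an attendance pattern that it does not state.

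**Working it through.** **Inputs.** Two-sided 0.05 (6.2). From 6.1: "17% response rate among controls"; 204 controls and 516 TCBD caregivers analysed, which is 80% of 255 and 645, total 900 (the total in 4.2); 75% of TCBD re-randomised; targets of 29.4% v 17% and D = 0.28 for enhanced v control. From 3.2: 1:1 re-randomisation.

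**Step 1: reproduce the stated power.** Implied enhanced n = 516 x 0.75 x 0.5 = 193.5.

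- Binary, pooled z test: power = Φ{[|p2 − p1| − 1.96 √(p̄(1 − p̄)(1/n1 + 1/n2))] / √(p1(1 − p1)/n1 + p2(1 − p2)/n2)}. With n1 = 204, n2 = 193.5, p̄ = (204 x 0.17 + 193.5 x 0.294)/397.5 = 0.2304, this is Φ[(0.124 − 0.0828)/0.0420] = 83.7%. With a continuity correction it is 80.5%. Both meet the stated >80%.
- CPaSS: Φ[0.28/√(1/204 + 1/193.5) − 1.96] = 79.7%, against a stated 80%.
- Cross-check, basic n = 516 − 193.5 = 322.5: 80.9% for 27.6% v 17% (pooled), 79.8% for D = 0.25.

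The figures reproduce, and they do so when half of 75% of **all** analysed TCBD caregivers are enhanced. Nobody analysed is taken to have missed Month 6.

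**Step 2: vary that assumption.** Let m be the share of the 516 who have a Month-6 classification. The documents do not give m. Enhanced n = 193.5 x m, unclassified = 516 x (1 − m), control held at 204.

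| m | Enhanced n | Unclassified at Month 12 | 29.4% v 17%, pooled | Same, continuity-corrected | D = 0.28 |
|---|---|---|---|---|---|
| 1.00 | 193.5 | 0 | 83.7% | 80.5% | 79.7% |
| 0.90 | 174.2 | 51.6 | 81.7% | 78.3% | 77.5% |
| 0.80 | 154.8 | 103.2 | 79.4% | 75.6% | 74.8% |

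Three attendance patterns show where m might lie:

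- The same 20% miss both visits: 645 x 0.80 x 0.375 = 193.5, so m = 1 and nothing changes.
- 20% miss each visit independently: 645 x 0.80 x 0.80 x 0.375 = 154.8, so m = 0.80.
- 10% miss each visit independently: 645 x 0.90 x 0.90 x 0.375 = 195.9, with 255 x 0.90 = 229.5 controls. Power is 86.0% (pooled) and 82.1% (D = 0.28), above the stated level.

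**Step 3: the basic group if unclassified caregivers are counted in it.** Take 27.6% for the classified basic caregivers (the 6.1 threshold) and an assumed rate r for the unclassified. Classified basic n = 322.5 x m.

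- m = 0.90: (290.25 x 0.276 + 51.6 x r)/341.85 = 25.7% at r = 15%, 27.2% at r = 25%.
- m = 0.80: (258 x 0.276 + 103.2 x r)/361.2 = 24.0% at r = 15%, 26.9% at r = 25%.

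The basic rate shifts by 0.4 to 3.6 points, out of a target difference of 27.6 − 17 = 10.6 points. Control is held at 17%. If control caregivers who miss Month 6 also respond less, the shift in the difference is smaller.

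**The case against.** The strongest reply is that little is left undefined. Caregivers start on basic TCBD and leave it only by re-randomisation, so someone never re-randomised is still on basic, and intention-to-treat keeps them in. That stands for the treatment they receive. It does not remove the unequal restriction on the enhanced group, and it does not say how they enter a second-stage comparison.

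A reader might go further than the documents allow in four ways:

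- *That the power calculation assumes no loss.* It does not: 6.1 removes 20% first.
- *That the stated power is an upper limit.* The 90% pattern above exceeds it. The retention text under 5.1.4 cites 80–90% compliance in earlier work, and 8.2 anticipates under 20% missing.
- *That these caregivers cannot be classified.* Section 5.1.3 allows the check-in by photograph or video. What is missing is a rule, not a means.
- *That the basic rate is diluted by 2 to 4 points.* That needs a response of about 15% among the unclassified, below even the control rate in 6.1. No passage supports it.

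It is also fair to say that attendance is the lesser selection. Every enhanced caregiver was a Month-6 non-user of the recommended restraint, by design, and this alone makes enhanced v control a comparison of unlike groups.

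**Conclusion.** The point holds as a gap in the second-stage analysis. Followed exactly, the plan compares an enhanced group selected on Month-6 attendance and Month-6 non-use with an unselected control group, and leaves every unclassified caregiver in basic. The two fully randomised contrasts, initial TCBD v control and basic v enhanced among those re-randomised, are sound.

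The effect on power is modest and conditional: none if the same caregivers miss both visits, and about 2 to 5 points if 10% to 20% of those analysed have no Month-6 status. Pooled power for the binary outcome stays at or above 80% down to about m = 0.825. The size of any distortion in the basic rate is unknown, because it turns on a response rate that the documents do not give.

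**What to change.** **Section 6.2.** Define two strategies, basic throughout and basic followed by enhanced for those found suboptimal at Month 6, and compare each with control. Count caregivers with no Month-6 classification in both strategies with weight 1, since they stay on basic under either. Count Month-6 responders in both with weight 1. Count re-randomised caregivers in their own strategy with weight 2, the inverse of the 1:1 probability. Use robust standard errors. Each strategy then represents the whole TCBD arm, as control represents the whole control arm, which deals with both selections.

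**Section 6.1.** Say which visit the 80% refers to. State the enhanced sample and its power as a range over Month-6 attendance among those analysed, and make clear which contrast each power figure belongs to.

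Using the Month-5 or Month-7 photographs to classify those who miss the visit is not proposed. It would change who is re-randomised, and a Month-7 set may arrive during the Month 7/8 session window.

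**Cost.** Somewhat more analysis work than the group comparison now planned, and possibly slightly less favourable stated power. No new data and no change to trial conduct.

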## **3.1 General Design**

The Tiny Cargo, Big Deal! (TCBD) emergency department (ED)-based intervention is designed to promote correct and consistent use of a size-appropriate child passenger restraint system on every trip. We will test the precision prevention intervention with a randomized, adaptive trial design. Caregivers (parents and legal guardians) of children who seek care for non-critical illness and injury at the Ann & Robert H. Lurie Children's Hospital of Chicago Emergency Department

# Emergency Medicine Prospective Protocol

will be screened. With this most recent IR modification (3/26/21), we will also add recruitment from Lurie Children's affiliate EDs (e.g., Central DuPage, Northwest Community) and Lurie Children's Immediate Care Centers (Lincoln Park and Northbrook). Eligible caregivers will have a child 6-months to 10-years-old and <55 inches tall who screen positive for suboptimal child passenger safety behavior or plans for premature transition to a less protective restraint in the coming year. Caregivers who agree to participate will be randomized to the basic TCBD intervention (an ED counseling session plus eHealth after ED discharge) or the control condition (usual ED care with discharge instructions relevant to the child's diagnosis and a car seat information sheet). At 6-months we will re-randomize caregivers in the intervention group alone who are not using a size-appropriate CRS to either continue basic TCBD or receive the enhanced TCBD, which includes one motivational interviewing (MI) session by phone in Month 7/8 and four instead of two text messages in Months 7-12.

## ***3.2 Allocation to Interventional Group***

After completing the baseline survey, all caregivers will be randomized into one of two groups: 1) TCBD intervention group, or 2) control group. Computerized, block randomization (block sizes from four to eight) will be applied to assign eligible caregivers to the TCBD intervention or control group in a 3:1 ratio. Blocks will be stratified by age groups related to child passenger safety recommendations (<2 years – rear-facing CRS, 2-4 years – forward-facing CRS, 5-10 years – booster seat) and the child passenger safety behavior that led to eligibility for study (not using the recommended restraint currently or planning a premature transition in the coming 6 months).

After the 6-month follow-up assessment, caregivers in the intervention group only who continue suboptimal CRS use will be re-randomized by computer in a 1:1 ratio to receive either the basic or enhanced intervention. The enhanced TCBD will include one additional motivational interviewing (MI) session by phone in Month 7/8 and one to two additional tailored text messages in Months 7-12 (total of 7 tailored tips during these months compared to 4 tailored tips for those in the basic TCBD). The extra text messages will be sent to those in the enhanced TCBD group until size-appropriate restraint use is observed. Caregivers receiving enhanced TCBD will be encouraged to obtain a free seat check with a certified child passenger safety technician (CPST) in the community. The primary outcomes (size-appropriate CRS use and CPaSS) will be assessed in-person at Months 6 and 12. The secondary outcome, the CPaSS trajectory, is a measure of correct and consistent restraint use in response to the intervention and will be assessed by scoring photographs submitted by caregivers (Months 1-5; 7-11).

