# Emergency Medicine Prospective Protocol

2) TCBD Intervention group --after taking the baseline survey, they will receive a brief motivational interviewing inspired counseling session with the research coordinator in addition to the same study handout sheet that the control group will receive. During the MI counseling session, participants will talk to the RC about how their child normally rides in their car, their goals for traveling safely with their child, and how they might reach these goals. Additionally, the intervention group will receive direct access to the study's mobile friendly website "site," Car Seat Compass. The site will provide parents with custom feedback based on their answers within the baseline survey regarding how their child normally rides in their vehicle and their general child passenger safety practices with that child. The site will give them answers to common questions about traveling with children as well. The control group will not have access to this site throughout the study. However, the control group will obtain access to the study website after the conclusion of their 12 month follow-up.

Both groups will participant in all of the Tiny Cargo check-ins and the 6- and 12 month follow up visits scheduled over the course of the study. Those elements of the study do not change based on the group someone is enrolled in.

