# Emergency Medicine Prospective Protocol

After completing the screening survey, the RA will determine if the participant is eligible to enroll in the part 2 baseline phase of the study based on a summary of their responses. Participants that are eligible will be notified of the opportunity to take part in an additional phase of the study and the RA will use a written informed consent document to obtain consent for further study participation. This process will occur in either the ED waiting room (a private space) or within the child's ED treatment room. Or remote consenting of part 2 will occur over the phone where the RA will go over the key points of the consent form. The informed consent includes 1) participation in the intervention study with baseline/follow-up assessments and 2) the collection of data using digital photographs. Prior to beginning any data collection with the participant, a trained research assistant will present and explain the comprehensive informed consent document, reviewing the study risks and participants' rights. After all questions are answered to the satisfaction of the participant, and after he/she signs the consent document, then data collection will begin. Participants will be given a copy of the consent form(s). The participant will provide signed consent of the parent permission form via Qualtrics for remote consenting.

For remote recruitment, after the subject completes the screening survey, the RC will determine if the participant is eligible to enroll in the study based on a summary of their responses. Participants that are eligible will be notified via phone, email, or text communication and will have the opportunity to enroll in part 2. The RC will follow the exact same procedures as in person recruitment for part 2 except all procedures will occur over the phone.

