## Blinding for purposes of data collection:

This is a unique single-blinded study where a portion of the study will include blinding of study team members. The blinding will not include the Principal Investigator or the Study Coordinator. Also, participants will know which group they are enrolled in as the consent form states the study groups as well as the extent of study involvement based on which group you are enrolled in.

The portion of the study that includes blinding are the monthly photo submissions that participants will send us via text message over the course of 12 months.

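### Block sizes of four to eight do not fit a 3:1 ratio except at 4 and 8, and the plan does not say that sizes vary at random or are hidden from enrolling staff

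*Combined protocol and SAP*

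**What the plan says.** Section 3.2 (Allocation to Interventional Group) describes the first randomization as done by computer, with "block sizes from four to eight) will be applied to assign eligible caregivers to the TCBD intervention or control group in a 3:1 ratio". It follows the baseline survey. "Blocks will be stratified by age groups related to child passenger safety recommendations", of which there are three, and by the behaviour that made the caregiver eligible ("not using the recommended restraint currently or planning a premature transition in the coming 6 months"). That makes 3 x 2 = 6 strata. The section does not list the sizes used, say whether they vary at random, or say how the sizes and the next assignment are concealed.

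On who does what:

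- **Eligibility and consent.** For remote recruitment, Section 4.5 (Consent process) says "the RC will determine if the participant is eligible to enroll in the study based on a summary of their responses", and Section 3 has the research coordinator hold the consent discussion by phone. In the emergency department, Section 9.4 gives consent to the project manager or research assistants.
- **Counselling.** Section 3.2 gives the intervention group a "brief motivational interviewing inspired counseling session with the research coordinator". Section 8.2, on audio recordings, gives this task to the research assistant.
- **Blinding.** Section 8.2 (Blinding for purposes of data collection) says "The blinding will not include the Principal Investigator or the Study Coordinator". Other staff may score photographs only of families they did not enrol, which implies that they know the arm of families they did enrol.

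**The concern.** There are two separate problems in one sentence.

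The first is that the allocation rule is not executable as written. Whoever programs the list must either drop sizes 5, 6 and 7 or choose an unstated rounding, and the reader cannot tell which ratio was delivered.

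The second is predictability. With 3:1 allocation, a block of 4 contains one control. Once that control appears, the rest of the block is known to be TCBD, and after three TCBD assignments the fourth is known to be control. Both stratification factors are available at screening, so the stratum can be known before consent. Remote recruitment draws on six months of visits, and the baseline survey may be finished within five business days, which leaves some room for the order of entry to vary. If a person who screens, consents or counsels could foresee the next arm, effort or timing could follow it. The resulting imbalance in unmeasured characteristics would not be corrected by the planned covariate adjustment. Random order and hidden block sizes are the usual protection, and the plan is silent on both.

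**Working it through.** **1. Which sizes hold 3:1** (sizes and ratio from Section 3.2). The TCBD count is 0.75 x size:

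| Size | 0.75 x size | Exact 3:1? |
|---|---|---|
| 4 | 3 | yes |
| 5 | 3.75 | no |
| 6 | 4.5 | no |
| 7 | 5.25 | no |
| 8 | 6 | yes |

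If all five sizes were used equally and rounded (an assumption for illustration), 5 becomes 4:1, 7 becomes 5:2, and 6 becomes either 4:2 or 5:1:

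- 6 as 4:2: (3+4+4+5+6)/(1+1+2+2+2) = 22/8 = 2.75:1
- 6 as 5:1: (3+4+5+5+6)/(1+1+1+2+2) = 23/7 = 3.29:1

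**2. Share of assignments known with certainty.** The documents give no figure for this, so there is none to reproduce. An assignment is certain when only one arm remains in its block, that is, when it lies in the final same-arm run. For a block of T TCBD and C control, the expected length of that run is T/(C+1) + C/(T+1). Divide by T + C. This assumes that the observer knows the block size and sees every earlier assignment in the stratum.

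- Size 4: (3/2 + 1/4)/4 = 1.75/4 = 43.75%
- Size 8: (6/3 + 2/7)/8 = 2.286/8 = 28.6%
- Size 12: (9/4 + 3/10)/12 = 2.55/12 = 21.25%

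Full enumeration of the arrangements gives the same three values.

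**3. Mixed sizes** (equal mix assumed, because the plan gives none).

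- 4 and 8, each size revealed: one third of participants fall in blocks of 4, so 1/3 x 43.75% + 2/3 x 28.6% = 33.6%.
- 4 and 8, sizes hidden: about 10%, by simulation with 24 to 150 participants per stratum.
- 8 and 12, sizes hidden: about 5.5% to 6%, by the same method.

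**4. How useful the knowledge is.** Always guessing TCBD is right 75% of the time. With known blocks of 4, the best guess is right with probability 0.75, 0.75, 0.75 and 1 at the four positions, a mean of 3.25/4 = 81.25%. For hidden mixes it is about 79% (4 and 8) and 77% (8 and 12).

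**5. Link to the planned group sizes** (Section 6.1). 204 + 516 = 720 = 0.8 x 900, which matches the stated retention. But 516/204 = 2.53, not 3. An exact 3:1 split of 720 is 180:540. Using the plan's 75% re-randomized 1:1, enhanced TCBD has 0.75 x 516/2 = 193.5 and basic has 516 - 193.5 = 322.5. At 180:540 these become 202.5 and 337.5. Two-sided 5% power against control:

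| Contrast | 204:516 | 180:540 |
|---|---|---|
| Basic, D = 0.25 | 79.8% | 77.3% |
| Enhanced, D = 0.28 | 79.7% | 78.0% |
| Basic, 27.6% vs 17% | 80.9% | 78.2% |
| Enhanced, 29.4% vs 17% | 83.7% | 81.9% |

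The 204:516 column agrees with the plan's claims of about 80% or more.

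**The case against.** The strongest reply is that this is a wording slip. The author may have meant sizes four and eight; then the ratio is exact and nothing drifts. That is plausible, but the text says otherwise and should be corrected. Ratio drift under random allocation would in any case not bias the comparison.

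A reader might also infer that a single unblinded coordinator can foresee 44% of assignments. The documents do not support this. They give a range of sizes, not a fixed 4; nowhere do they say that staff know the size; and they spread consent and counselling over research coordinators, research assistants and a project manager. Staff are treated as blinded for families they did not enrol. The unblinded Study Coordinator is not shown to be the person who consents every family or who tracks every stratum. Even in that worst case, 1.5 of the 1.75 certain assignments per block are TCBD, and the best guess improves on always guessing TCBD by about 6 points.

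A reader might further infer that rounding would upset a sample size built on 3:1. It was not built on 3:1: Section 6.1 uses 2.53:1, and a rounded 2.75:1 would lie closer to that than 3:1 does.

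Safeguards exist. Randomization comes after consent and the baseline survey, eligibility rests on the caregiver's own screening answers, and the caregiver may finish the survey on a personal device. Section 6.2 plans balance checks and adjustment, which deal with measured differences only. What remains is that the plan does not state the two features, random order and hidden sizes, that would bring the figure down to about 10%.

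**Conclusion.** The point holds in two parts. It is certain, by arithmetic on Section 3.2 alone, that sizes 5, 6 and 7 cannot carry a 3:1 ratio, so the allocation rule is incomplete or misworded. It is also clear that the section does not say whether block sizes vary at random or are concealed, although some people in the recruiting pathway may know past assignments.

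The possible size of the second problem depends on what was actually programmed: from about 10% of assignments certain (equal mix of 4 and 8, hidden) up to 44% (fixed at 4, known, one observer of the whole stratum). The upper figure is a ceiling, not a description of this trial. The documents support neither a coordinator who knows all past assignments nor planned group sizes that rest on 3:1. This is a minor point, worth correcting because the correction is cheap.

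**What to change.** Replace the block-size phrase in Section 3.2 with wording to this effect: permuted blocks whose sizes are multiples of 4 (for example 8 and 12, or 4 and 8), in random order, with the sizes and the allocation list withheld from all staff who screen, consent or counsel, within the existing six strata. Add a sentence on how each assignment is concealed until it is released.

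Recruitment was anticipated from October/November 2019 and the text carries a modification of 3/26/21, so randomization may well have begun. If so, document the sizes actually used, any rounding applied, and who had access to the list, and report this with the results.

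The cost is one sentence and a setting in the randomization program, or a short note if allocation is already running. Larger blocks allow a slightly larger imbalance if a stratum ends mid-block.

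Separately, reconcile the 204:516 in Section 6.1 with the 3:1 in Section 3.2, and restate the power for whichever ratio is used.
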